To fill this critical knowledge gap, we propose a randomized, controlled 12-week trial using incentives to reduce COC use, with an additional 24 weeks of follow up. Over 5 years, subjects will be randomly assigned to one of three groups (n=66 completers/group): 1) high value incentives for COC abstinence in which frequency of COC use is expected to be substantially reduced or eliminated, 2) low value incentives for COC abstinence in which frequency of COC use is expected to be reduced or 3) a non-contingent control group, in which frequency of COC use is expected to remain stable. Three specific aims are proposed:

First, this study seeks to demonstrate that reduced COC use improves physiological and biochemical indicators (i.e., biomarkers) of cardiovascular function. Improvements in cardiovascular function will be assessed with physiological measures of cardiovascular fitness (e.g., peripheral arterial tonomotry) and biomarkers of endothelial (e.g., endothelin-1) and platelet (e.g., soluble CD40L) function.

Second, this study seeks to demonstrate that reduced COC use improves physiological indicators and biomarkers of immune function. Improvements will be assessed with a physiological measure (i.e., delayed-type hypersensitivity) and biomarkers of immune function (e.g., tumor necrosis factor- α , microbiome indicators).

Third, this study seeks to demonstrate that reduced COC use improves psychosocial function. Psychosocial improvements will be assessed with standardized observer and self-reported measures of mental health, drug use and risky behavior, as well as validated and sensitive cognitive behavioral tasks.

Our overarching hypothesis is that individuals assigned to the active treatment conditions (i.e., those who reduce their COC use) will display health improvements compared to individuals assigned to the noncontingent control group both during and after treatment. A "dose-response" is expected whereby individuals assigned to the high value condition will display greater reductions in COC use, and consequently greater improvements, relative to the low value group. We further hypothesize that 1) individuals assigned to active treatment conditions will display improvements from baseline through treatment completion and into follow up and 2) biomarker improvements will predict physiological outcomes.

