urine sample outcome. Subjects will earn \$60 for each Post Intervention visit. Subjects will also earn \$15 for completing a follow up visit to have their DTH response measured 48 hours after their 4, 12 and 24 Week Post visit. To increase completion rates, subjects will receive half of the visit payment (e.g., \$30 for the 6 Week visit) at the end of each study visit. The remaining half will be paid upon study completion. If a subject completes all study visits, he or she can earn approximately \$1,230 in study payments.

Data Analysis

The statistical significance criterion is $p \le 0.05$.

Aim 1: To demonstrate that reduced COC use improves physiological and biochemical indicators (i.e., biomarkers) of cardiovascular function. Time-and group-varying weekly number of BE-negative urine samples will be analyzed as the primary predictor of cardiovascular outcomes (e.g., endothelin-1 levels) using generalized linear mixed models (GLMM; Stata 14, College Station, TX). All models will be constructed using intent-to-treat analyses including non-completing subjects, whereby the group to which the participant is randomized will be utilized. GLMM are particularly well suited for analyses of longitudinal data, as they allow for multiple observations over time, correlations among observations within an individual subject, for subjects measured at different time points and for baseline covariates (e.g., sex; age; race) and covariates that change over time (e.g., alcohol use). Although GLMM allow for missing data, any missing data will first be tested to determine whether they are missing at random or missing not at random (MNAR). Any data MNAR will be subject to multiple imputation.

Aim 2: To demonstrate that reduced COC use improves physiological indicators and biomarkers of immune function. Time- and group-varying weekly number of BE-negative urine samples will be analyzed as the primary predictor of immune outcomes (e.g., IL-10 levels) using GLMM. Other details are the same as for cardiovascular outcomes.

Aim 3: To demonstrate that reduced COC use improves psychosocial function. Time-and groupvarying weekly number of BE-negative urine samples will be analyzed as the primary predictor of psychosocial outcomes (e.g., other drug use) using GLMM. Other details are the same as for cardiovascular outcomes.

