The physiological and biological cardiovascular function tests will be the primary outcome measures from the intervention and follow up period because cardiovascular insult is one of the most troubling health problems associated with COC use. As such, previously published data regarding the effects of COC use reduction on endothelin-1 levels were used to estimate the necessary sample size for this trial. In that study, reduced COC use significantly reduced endothelin-1 levels (estimated effect size [r]=0.28), approximately half of that observed after COC abstinence. Although cardiovascular measures will be our primary outcome, it is important to note that comparable effect sizes have been observed for indicators of psychosocial outcomes as a function of reduced COC use. Effect sizes observed following COC use reduction in those studies ranged from approximately 0.15 to 0.45 for statistically significant outcomes (e.g., improved ratings of "Good Functioning" after treatment, reduced alcohol use at the end of treatment). Enrolling 66 completing subjects in each group will give us 80% power (alpha=0.05) to detect effect sizes (r) as small as 0.14 when comparing

data across the three groups. This sample size will also allow us to conduct exploratory analyses and control for any relevant biological variables that might influence outcome. Dependent variables are continuous, increasing our power relative to using dichotomous variables.

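### The hypothesis and sample size concern the three randomised groups, but no group test is defined for any health outcome, and the primary predictor is a post-randomisation urine count that does not exist at follow-up visits

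*Combined protocol and SAP*

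**What the plan says.** The overarching hypothesis in section 1 is that subjects in the active groups "will display health improvements compared to individuals assigned to the noncontingent control group both during and after treatment", with a graded response from low to high incentive value. The Sample Size Justification in section 7 claims 80% power with 66 completers per group "to detect effect sizes (r) as small as 0.14 when comparing" "data across the three groups". It also says that the cardiovascular tests "will be the primary outcome measures from the intervention and follow up period".

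The Data Analysis part of section 7 is built on a different variable: "Time-and group-varying weekly number of BE-negative urine samples will be analyzed as the primary predictor of cardiovascular outcomes". Aims 2 and 3 repeat this for immune and psychosocial outcomes. Randomised group appears there in the description of the count as group-varying and in one further sentence: "All models will be constructed using intent-to-treat analyses including non-completing subjects, whereby the group to which the participant is randomized will be utilized". The same paragraph says the models can carry "covariates that change over time (e.g., alcohol use" as an example.

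Under Defining Reduction in Frequency of COC Use, the count is the number of negative samples per week out of three, from thrice-weekly sampling during the 12-week intervention. Table 1 shows one urine screen at each post-intervention visit. Other Analyses lists self-report (TLFB, ASI) and whole-trial urine summaries as further indicators of use.

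**The concern.** The hypothesis and the power statement concern arms formed by randomisation. The defined analysis concerns behaviour that follows randomisation. Subjects who give more negative samples may differ in other ways that affect endothelin-1, and keeping everyone in the assigned arm does not remove that from the count's coefficient. Entering group beside the count does not help either: the group coefficient is then adjusted for the variable through which the incentives are meant to act, so it is not the effect of assignment.

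Time-varying alcohol use raises the same difficulty. It is offered as a possible covariate, while the Sample Size Justification cites "reduced alcohol use at the end of treatment" among the effects seen when cocaine use falls.

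The trial is meant to supply prospective evidence that reduced use improves health, and Other Analyses describes reductions in use as producing benefit. As written, the only defined primary analysis cannot carry that claim with the protection of randomisation. The comparison that could has no fixed contrast or visit, so these would be chosen after the data are seen. At follow-up, the primary model lacks its predictor.

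**Working it through.** **1. The plan's own power figure.** Inputs from the Sample Size Justification: N = 3 × 66 = 198, alpha 0.05, r = 0.14, stated power 80%. For a one-way comparison of three groups, λ = N·r²/(1 − r²) = 198 × 0.0196/0.9804 = 3.96; with 2 and 195 df the power is 40.6%. A two-sided correlation test on 198 gives 50.3%. About 80% can be reached with a repeated-measures group test under added assumptions, for example 4 measurements with correlation 0.2 (79.6-80.5%). The plan names no test, number of measurements or correlation, so the figure cannot be traced to an analysis. This does not show it to be wrong.

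**2. Where the count exists (Table 1).**

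| Outcome | Post-baseline visits during intervention | After intervention | Share without a defined count |
|---|---|---|---|
| Biomarkers, including endothelin-1 | weeks 6, 12 | 4, 12, 24 weeks post | 3 of 5 |
| PAT, ECG | week 12 | 4, 12, 24 weeks post | 3 of 4 |

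**3. Confounding, illustration only.** The confounder strengths have no source in the documents. Assumptions: 66 per arm; no true effect of use; arm explains 10-20% of the variance in use; week-to-week correlation of use within arm 0.5-0.9; one stable unmeasured factor correlated 0.2, 0.3 or 0.4 with both count and outcome; no other covariates. Outcomes at baseline and weeks 6 and 12 were analysed with random-intercept models, 3000 trials per scenario, nominal level 5%. Outcome ICC is the correlation between two visits of one subject.

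| Test | Outcome ICC | Factor 0.2 | Factor 0.3 | Factor 0.4 |
|---|---|---|---|---|
| Count alone | 0.5 | 6.2-6.8% | 12.4-14.5% | 30.4-35.4% |
| Count alone | 0.8 | 4.9-5.7% | 6.6-8.9% | 12.3-14.1% |
| Count beside group | 0.5 | 6.3-7.3% | 13.2-16.4% | 31.1-41.5% |
| Count beside group | 0.8 | 4.8-6.3% | 6.4-9.0% | 12.1-15.3% |

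Across all scenarios the baseline-adjusted randomised-group test rejected in 4.2-5.5%, and a purely within-subject count term in 4.1-5.6%. The excess therefore comes from differences between subjects.

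**4. Power of a group test.** Assume that the cited r = 0.28 for endothelin-1 is fully causal and that arm explains a share R² of the variance in use. Then r_group = 0.28·√R² and λ = N·r_group²/(1 − r_group²), tested on 2 df. At outcome ICC 0.5:
- Baseline adjustment multiplies the residual variance by 1 − 0.5² = 0.75.
- Averaging weeks 6 and 12 as well makes it 0.5 + 0.25 − 0.25 = 0.5.
- λ is divided by these factors.

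| R² | r_group | λ | One visit | Baseline-adjusted | Adjusted, mean of two visits |
|---|---|---|---|---|---|
| 0.1 | 0.089 | 1.56 | 18% | 23% | 33% |
| 0.2 | 0.125 | 3.15 | 33% | 43% | 60% |
| 0.3 | 0.153 | 4.77 | 48% | 60% | 79% |
| 0.4 | 0.177 | 6.41 | 61% | 74% | 90% |

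If all 300 enrolled subjects gave full data (an upper bound), the three power columns run 26-80%, 33-90% and 48-98%. At ICC 0.8 and N = 198 the last two run 44-97% and 58-100%. For the exposure model, λ = 198 × 0.0784/0.9216 = 16.84 on 1 df, giving 98.3%.

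**The case against.** The strongest reply is that the exposure model is the design. Section 2, the aims and the primary outcome in section 17 all speak of the influence of reduced use, and section 7 says the spread of response across arms will serve to predict health. That stands: the exposure model belongs in the plan. It does not supply a test for the group hypothesis in section 1.

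Second, group is not absent: the count is described as group-varying and the intent-to-treat sentence covers all models. This suggests that group enters somehow, but it names no term, contrast or visit. The one clear use of assignment as an explanatory factor is for frequency of cocaine use, which is not a health outcome.

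Third, follow-up has other exposure measures: a urine screen, TLFB, ASI and whole-trial urine summaries. The last three are listed under Other Analyses, and nothing says which, if any, replaces the primary predictor.

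Fourth, the alcohol sentence describes what such models allow and commits to nothing. That is fair, and in the exposure model alcohol could be a legitimate confounder. The caution applies to the group model.

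Fifth, the simulated rates depend on unsourced assumptions. That stands; they show direction, and the two gaps do not rest on them.

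Last, dropout can bias a group test too. Section 4 plans 198 completers of 300 enrolled, so 102/300 = 34% may not complete. In an illustration with assumed outcome-related dropout differing by arm, a complete-case group test rejected in 10-31% of null trials. The group model therefore needs its own missing-data statement.

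**Conclusion.** The concern holds, and the plan must be changed. Two gaps follow from the text alone: the health hypothesis about randomised groups has no term, contrast or visit, and the primary predictor has no definition at 3 of 5 post-baseline biomarker visits and 3 of 4 PAT and ECG visits. A third point follows from the design: the count's coefficient is a non-randomised association, whatever analysis set is used.

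The size of any false-positive excess is unknown. It is negligible if the shared factor is weak and modest if the marker is stable within subjects. Under the assumptions above it reaches about 35% for the count alone, or 42% with group beside it. The group test's validity also depends on how missing data are handled.

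**What to change.** In Data Analysis, section 7:

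- **Add a group model for Aims 1-3.** Use a GLMM of the outcome (endothelin-1 for Aim 1) on randomised group, visit and group-by-visit in all randomised subjects. Adjust for the baseline outcome and the three urn factors (sex, age, baseline days of cocaine use). Include neither the count nor alcohol use after randomisation.
- **Name the tests.** Give the contrast and visit that test the section 1 hypothesis during treatment, and those that test it after treatment. State their order and how missing outcomes are handled.
- **Keep the count model** as the analysis of the reduced-use objective, adjusted for baseline outcome and baseline cocaine use, and label it a non-randomised exposure analysis. Optionally split the count into subject mean and within-subject change, so that stable confounding can be seen.
- **Define exposure at post-intervention visits**, for example from the urine screen or TLFB.
- **State which analysis ranks first.** That choice is the sponsor's.

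The cost is wording and one more model per outcome on data already collected, with no change in conduct. The drawback to state in the plan is that incomplete response to the incentives dilutes the group contrast. Its power could be as low as 18-33% at one unadjusted visit if arm explains 10-20% of use, against about 98% for the exposure model at r = 0.28. That is a reason to report both.

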Defining Reduction in Frequency of COC Use. Subjects will provide observed urine samples thrice weekly (i.e., Monday, Wednesday and Friday) during the 12-week intervention. This thrice weekly urine collection schedule was selected based on the detection time of BE in urine (i.e., up to 72 hours after use; 89) and because the study on which our incentive schedule is based used thrice weekly testing. All urine samples will be coded as positive or negative using qualitative urine BE screens that have a 300 ng/ml cutoff, a criterion used in many recent clinical trials and the criterion used by Higgins and colleagues (Higgins et al., 2007). Using this approach will allow estimates of the levels of reduction observed in each of the three groups (see above).

The number of BE-negative urine samples provided across each week of the trial, out of a maximum of three each week, will be calculated for each subject to determine how group assignment impacted frequency of use. *Experts recently recommended that frequency of use, rather than quantity of use, be the target for reduction (Kiluk et al., 2016).* Overall percentage and number of BE-negative urine samples across the trial will also be calculated. Subjects are likely to vary in their response to alternative reinforcers, especially between the three conditions, which will provide a range of scores that can be used to predict health outcomes. This variability should also permit exploratory analyses (see below) that will reveal threshold levels of change (e.g., 25%, 50%, 75% negative samples) that are associated with beneficial health outcomes.

Individual Counseling

To provide some benefit to all subjects in addition to health screening and monetary remuneration, all subjects will receive supportive behavioral therapy which provides clinical recommendations for reducing or ceasing COC use. Manual-guided treatment (the Substance Abuse and Mental Health Services Administration's Counselor's Treatment Manual: Matrix Intensive Outpatient Treatment for People with Stimulant Use Disorders) will be conducted weekly with a masters or graduate level psychologist, social worker or counselor, who will remain blind to assigned conditions. Based on our current experience, this counseling will also enhance retention.

Measures

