Table 1. Outline of data collection frequency. An X indicates when a test will be done, with the exception of the 12-week intervention, where frequency is described instead. "3 Days/Week" indicates measures that will be completed at each of the three weekly visits made by subjects during the intervention (36 total data points/each). "Weekly" indicates measures that will be completed once per week during the intervention (12 total data points/each). "Weeks 4, 8, 12" indicates measures that will be completed at 4-week intervals during the intervention (three total data points/each). "Weeks 6, 12" indicates measures that will be completed at 4-week intervals during the intervention (two total data points/each). Week 12 indicates measures that will be completed during the final week of the protocol (one data point/each).

Measure (Domain;	Baseline	12-Week	4 Weeks	8 Weeks	12	24
CV=Cardiovascular,		Intervention*	Post	Post	Weeks	Weeks
IM=Immune;					Post	Post
PS=Psychosocial)						
Height (General Health)	Х					
Drug Urine Screens (PS)	X	3 Days/Week	Х	Х	Х	Х
Pregnancy Screen	Х	Weeks 4, 8, 12	Х	Х	Х	Х
Weight (General Health)	X	3 Days/Week	Х	Х	Х	Х
Breath CO (PS)	X	3 Days/Week	Х	Х	Х	Х
Vital Signs (CV)	Х	3 Days/Week	Х	Х	Х	Х
SMHSQ (PS)	Х	3 Days/Week	Х	Х	Х	Х
HAMD (PS)	Х	Weekly	Х	Х	Х	Х
Cognitive Battery (PS)	Х	Weekly	Х	Х	Х	Х
HRBS (PS)	Х	Weekly	Х	Х	Х	Х
Adverse Events (General	X	Weekly	Х	Х	Х	X
Health)						
Biomarkers (CV, IM)	X	Weeks 6, 12	Х		Х	Х
DTH (IM)	Х	Weeks 6, 12	Х		Х	Х
ASI (PS)	X	Weeks 4, 8, 12	Х	Х	Х	Х
PROMIS (General Health)	X	Weeks 4, 8, 12	X	X	Х	X
TLFB (PS)	X	Weeks 4, 8, 12	Х	Х	Х	Х
PAT (CV)	X	Week 12	Х		Х	Х
SCID-5 (PS)	X	Week 12	Х		Х	Х
SIPC (PS)	X	Week 12	Х		Х	Х
ECG (CV)	X	Week 12	Х		Х	Х
Microbiome (IM)	X	Week 12				
Additional Biomarkers (IM) for	X	Week 12				
analysis at Temple						
Lab Chemistries (General	X	Week 12	Х		Х	X
Health)						

Subjects will earn \$60 for the Baseline visit. Subjects will earn \$15 for 3 Days/Week visits, \$30 for Weekly visits, \$45 for 4 Week visits and \$60 for the 6 Week visits, in addition to any payment they receive for their

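### The raw weekly BE-negative count, as the one named primary predictor, blends within-person change with stable differences between people and can indicate benefit when reduced use does nothing

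*Combined protocol and SAP*

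**What the plan says.** The Data Analysis part of Section 7 states for Aim 1: "Time-and group-varying weekly number of BE-negative urine samples will be analyzed as the primary predictor of cardiovascular outcomes". Aim 2 repeats it ("weekly number of BE-negative urine samples will be analyzed as the primary predictor of immune outcomes (e.g., IL-10 levels) using GLMM"), and Aim 3 is worded the same way. The predictor is defined earlier in Section 7, under the heading on reduction in frequency of use: "The number of BE-negative urine samples provided across each week of the trial, out of a maximum of three each week". It is a raw count from 0 to 3.

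The inference wanted is causal: "To demonstrate that reduced COC use improves physiological and biochemical indicators (i.e., biomarkers) of cardiovascular function". The plan also intends differences between people to inform the estimate: "Subjects are likely to vary in their response to alternative reinforcers, especially between the three conditions, which will provide a range of scores", to be used for predicting health outcomes.

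On randomisation, Data Analysis says: "All models will be constructed using intent-to-treat analyses including non-completing subjects, whereby the group to which the participant is randomized will be utilized". No arm term, arm contrast or interaction is written down, and the description of the count as group-varying is not explained. Covariates are given as examples, "for baseline covariates (e.g., sex; age; race) and covariates that change over time (e.g., alcohol use", and the baseline value of the outcome is not among them. Nothing in the document mentions a person mean, centring or a deviation term.

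Section 17 names endothelin-1 as the primary outcome. Table 1 schedules biomarkers at baseline, Weeks 6 and 12, and 4, 12 and 24 weeks after the intervention. Peripheral arterial tonometry (PAT) and ECG have baseline, Week 12 and the same three later visits. The plan does not say which of these rows enter the models.

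**The concern.** The count is measured after randomisation and reflects how each person responded. In a random-intercept model with one raw time-varying term, the coefficient is a precision-weighted average of two slopes. The within-person slope asks whether a person's outcome is better at visits when that person gives more negative samples. The between-person slope asks whether people who give many negatives have better outcomes than people who give few. The second slope carries every stable difference between those groups of people that the covariates do not capture.

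A significant coefficient would be read as evidence that reducing use improves endothelin-1, when it might show only that people able to abstain are healthier. This affects the primary outcome and all three aims. The trial's stated purpose is to support reduced use as a treatment endpoint, so the distinction matters to its main conclusion.

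**Working it through.** **The plan's own figure.** The plan gives none for this coefficient. The nearest is the 80% power at r = 0.14 with 66 completers per group in Sample Size Justification. A single-time-point correlation test at N = 198 gives 50%. Repeated-measures variants run from 44% to nearly 100%, depending on the number of measures and their correlation, which are not stated. The figure may come from such a calculation. Nothing below depends on it.

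**Weight on the between-person slope.** With n visits, unit variances, and intraclass correlations ICCx (count) and ICCy (outcome), the information per subject is:

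- within = (n − 1)(1 − ICCx) / (1 − ICCy)
- between = [n·ICCx + (1 − ICCx)] / [(1 − ICCy) + n·ICCy]

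The between-person weight is between / (within + between). The ICCs are assumed. With n = 2 (Weeks 6 and 12):

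| ICCx | ICCy | within | between | between-person weight |
|---|---|---|---|---|
| 0.7 | 0.5 | 0.3/0.5 = 0.600 | 1.7/1.5 = 1.133 | 65% |
| 0.5 | 0.5 | 0.5/0.5 = 1.000 | 1.5/1.5 = 1.000 | 50% |
| 0.7 | 0.7 | 0.3/0.3 = 1.000 | 1.7/1.7 = 1.000 | 50% |
| 0.5 | 0.7 | 0.5/0.3 = 1.667 | 1.5/1.7 = 0.882 | 35% |

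Measures taken weekly are much less exposed. With n = 12, ICCx 0.7 and ICCy 0.5 give 6.6 within and 8.7/6.5 = 1.338 between, a weight of 17%. ICCx 0.5 and ICCy 0.7 give 18.33 and 6.5/8.7 = 0.747, a weight of 4%.

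**False significance with no effect of use.** Simulated trials had N = 198, a 0–3 count, a random-intercept model, two-sided 5% level and ICCs of 0.5–0.7. The person-level correlation between abstinence and the outcome was set at 0.14 or 0.28. These values are borrowed from the sample-size section as a scale only. There, 0.28 is a published effect of reduced use on endothelin-1 and 0.14 is the detectable effect. Neither measures confounding. The baseline row carries a count of 0, because Section 4 requires a cocaine-positive urine at entry.

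| Rows analysed | correlation 0.14 | correlation 0.28 | within-person term |
|---|---|---|---|
| Weeks 6 and 12 only | about 9–19% | about 28–54% | about 5% |
| Baseline row added | about 7–11% | about 15–29% | about 5% |

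**Does arm in the model help?** A further set had outcome ICC 0.6 and Weeks 6 and 12 only. False findings in the direction of benefit (nominal 2.5%) at 0.28 were 43% without arm and 48% with it. At 0.14 they were 14% and 15–16%. An arm covariate absorbs the part of the between-person variation that randomisation created and leaves the self-selected part within each arm. Adjusting for the baseline outcome left 21% at 0.28. The randomised-arm contrast itself stayed at about 2–3%.

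**Limits of a within-person term.** If only Weeks 6 and 12 are used, a participant with three negatives at both visits has deviations 3 − 3 = 0 and contributes nothing to the slope. With a baseline count of 0, the mean is (0 + 3 + 3)/3 = 2 and the deviations are −2, +1 and +1. The term is also not safe against everything. With an assumed time-varying confounder (residual correlation 0.4), it gave false benefit in 69% of trials. With a common 0.2 SD improvement after baseline and no time term, it did so in 71%.

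**The case against.** The strongest reply is that the trial is randomised, the Background frames its main hypothesis as a comparison of groups, and the counts are expected to differ by arm. Some of the between-person variation is therefore created by design and is unconfounded. This is true, but the plan writes no analysis that isolates that part, and entering arm as a covariate removes it.

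A second reply is that Table 1 schedules a baseline visit and follow-up visits, so more than two rows may be analysed. This also stands in part. A baseline row roughly halves the problem at 0.28 but does not remove it. Follow-up visits have one urine screen each, so the count out of three is undefined there.

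Third, the error rates rest on assumed ICCs and an assumed confounding correlation. That is right. Only the mechanism and its direction are firm.

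A reader might go further and infer that the between-person part carries most of the weight for endothelin-1, or that the PAT and ECG coefficients are wholly between-person. The documents support neither. The two-visit weight is 35–65% across the assumed range. The PAT and ECG statement holds only if the baseline row is left out, and the plan does not say that it is.

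**Conclusion.** The concern holds. As written, the primary models for all three aims rest on a coefficient that mixes a person's own change with stable differences between people, and it can indicate benefit when there is none. For endothelin-1 at N = 198, chance significance rises from 5% to about 9–19% (correlation 0.14) or 28–54% (0.28) with Weeks 6 and 12 alone, and to about 7–11% or 15–29% with a baseline row. These figures assume ICCs of 0.5–0.7 and are illustrations, not estimates for this trial. The absence of a split is read from the plan's silence, and the undefined term group-varying could mean a group interaction. Arm terms would not remove the within-arm, between-person part.

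A reader might also infer that splitting the count would by itself justify the causal claim. It would not: the within-person term is free of stable confounding but not of time-varying confounding. Only the randomised comparison is protected by design.

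**What to change.** In the Data Analysis models for all three aims:

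- State which rows enter. Include the baseline outcome row with a count of 0, and model time as categorical.
- Replace the raw count with two terms: the subject's mean count over the analysed rows and the visit's deviation from it. Report the mean term only as an association between people.
- Report alongside it the randomised-arm comparison that the Background hypothesises, identified as the only contrast protected by design.
- Treat the within-person term as supportive evidence, and do not rest the claim that reduced use improves an outcome on the blended count.
- If the baseline row is left out for a measure with one on-treatment visit, label its result a between-person association.

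The change needs SAP wording and derived variables, with no new data. It costs precision. For an assumed 0.10 SD effect per negative sample, power falls from about 76–82% (raw count) to 69–73% (within-person term) with a baseline row, and from about 61–70% to 35–44% without one. The arm contrast may have low power. With simulated mean counts of about 1.9 (high value) and 0.8 (control), the same effect implies only 0.10 × (1.9 − 0.8) = 0.11 SD between those arms, and power in that scenario was about 7–12%.
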